### **10.5.3.2 New Vertebral Fracture, New or Worsening Vertebral Fracture, and Multiple New or Worsening Vertebral Fracture**

The primary efficacy analysis set for vertebral fracture as described in [Section 7.1](#) will be used for the analyses of following efficacy endpoints: subject incidence of new vertebral fracture through Month 12, subject incidence of new or worsening vertebral fracture through Month 12 and Month 24, subject incidence of multiple new or worsening vertebral fracture through Month 12 and Month 24. The above subject incidences between subjects in the treatment group and subjects in the control group will be compared using a logistic regression model adjusting for age strata as described in [Section 10.5.1.1](#). The number and percentage of subjects with  $\geq 1$  above specified vertebral fracture will be summarized by treatment group for first 12-month of double-blind period and for 24-month study period. The adjusted odds ratio and the corresponding 95% confidence interval will also be provided.

The efficacy analysis set for vertebral fracture during 24-month study period as described in [Section 7.11](#) will be used for the analysis of subject incidence of new vertebral fractures between Month 12 and Month 24. The number and percent of subjects with new vertebral fracture between Month 12 and Month 24 in this efficacy analysis set will be summarized by treatment group. The treatment comparison will be done using a logistic regression model as described in [Section 10.5.1.1](#). Due to the lack of randomization at Month 12, the comparability between the two arms is not ensured and therefore the analysis is more susceptible to bias.

### **10.5.3.3 Percent Changes in Lumbar Spine, Total Hip and Femoral Neck BMD by DXA**

The primary efficacy subset for BMD described in [Section 7.6](#) will be used for the analyses of percent changes from baseline in lumbar spine, total hip and femoral neck by DXA at month 12, 24, and 36.

The treatment comparisons of the BMD in lumbar spine, total hip and femoral neck at months 12 and 24 will be analyzed using the ANCOVA model described in [Section 10.5.1.5](#) with LOCF imputation as the primary analysis. Descriptive summary of

observed DXA values at Month 36 will be provided without LOCF. Graphical displays to assess the model will include response versus fitted values, response versus standardized residuals and a normal probability plot of the standardized residuals. The sensitivity analyses include the repeated measures model as described in [Section 10.5.1.6](#), where each body site is estimated using a separate repeated measures model.

Absolute values and change from baseline for BMD will also be summarized descriptively by time point and machine type.

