#### **Bone Mineral Density by DXA**

For a body site (lumbar spine, total hip and femoral neck), percent changes of BMD from baseline to Month 12 will be compared between treatment groups using an ANCOVA model with treatment group, stratification factor (age), presence or absence of severe vertebral fracture at baseline, baseline BMD at the same body site as the endpoint, machine type, interaction of baseline BMD and machine type as independent variables. Any missing BMD value at Month 12 will be imputed by the last post-baseline BMD value that is prior to Month 12.

Percent changes of BMD from baseline to Month 24 and 36 during the primary analysis period will be analyzed using the same ANCOVA approach. Any missing values at Months 24 or 36 will be imputed by the last post-Month 12 value that is prior to the time point of interest.

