### **4.2 Secondary Endpoints**

The secondary efficacy endpoints include the following:

*During the primary analysis period:*

- Subject incidence of nonvertebral fracture at primary analysis
- Subject incidence of all fractures (nonvertebral fracture and new or worsening vertebral fracture) at primary analysis
- Subject incidence of new or worsening vertebral fracture through Month 24
- Subject incidence of major nonvertebral fracture (pelvis, distal femur, proximal tibia, ribs, proximal humerus, forearm, and hip) at primary analysis
- Subject incidence of hip fracture at primary analysis
- Subject incidence of multiple new or worsening vertebral fractures through Month 24
- Subject incidence of clinical fracture (nonvertebral fracture and clinical vertebral fracture) through Month 24

- Subject incidence of nonvertebral fracture through Month 24
- Subject incidence of hip fracture through Month 24
- Subject incidence of clinical vertebral fracture through Month 24
- Percent change from baseline in BMD at the lumbar spine, total hip, and femoral neck at Months 24, and 36

*During the 12-month double-blind ALN-controlled study period:*

- Subject incidence of clinical fracture (nonvertebral fracture and clinical vertebral fracture) through Month 12
- Subject incidence of new vertebral fracture through Month 12
- Subject incidence of all fractures (nonvertebral fracture and new or worsening vertebral fracture) through Month 12
- Subject incidence of nonvertebral fracture through Month 12
- Subject incidence of hip fracture through Month 12
- Subject incidence of major osteoporotic fracture (hip, forearm, humerus, and clinical vertebral) through Month 12
- Subject incidence of clinical vertebral fracture through Month 12
- Percent change from baseline in BMD at the lumbar spine, total hip, and femoral neck at Month 12

*For the overall study period:*

- Subject incidence of nonvertebral fractures at final analysis
- Subject incidence of major nonvertebral fracture (pelvis, distal femur, proximal tibia, ribs, proximal humerus, forearm, and hip) at final analysis
- Subject incidence of hip fracture at final analysis

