### **9.2.3 DXA or QCT Endpoints**

Missing baseline values for endpoints by DXA or QCT at any anatomical site will not be imputed. Missing post-baseline values will be imputed using LOCF approach (by carrying forward the last nonmissing post-baseline value prior to the missing value from the same anatomical site). For the open-label period endpoints, only the open-label period value will be used for imputation, the values in the double-blind period will not be carried forward into open-label period. The LOCF imputation will be done up to Month 36. Missing post-baseline data will not be imputed when repeated measures model is employed as a sensitivity analysis.

If a subject has values from different DXA machine types (ie, Hologic and Lunar) or QCT machine types only those values that are collected from the same machine type as the baseline will be used for analyses and imputation. For anatomical sites that can be measured on different body sides (ie, left and right), only those values that are collected from the same body side as the baseline will be used for analyses and imputation.

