### 13. Appendices

#### 13.1 Technical Detail and Supplemental Information Regarding Statistical Procedures and Programs

##### 13.1.1 Visit Windows

Per protocol, all monthly study visits up to Month 13 have a  $\pm 7$ -day window. Following the 12-month double-blind ALN-controlled study period, study visits have a  $\pm 14$ -day window. To allow for variations in scheduling, the following sets of visit windows will be used to assign evaluations to a most appropriate nominal visit for analysis. Furthermore, there will be no gaps between visit windows in order to include as many data points as possible for summarization.

Regardless of the width of the visit window, if more than 1 visit falls within the defined window, the result from the visit closest to the target day will be used. If 2 evaluations are of the same distance from the target day, the result from the later visit will be used. If more than one evaluation on the same date and time, the average of the results will be used. Only laboratory results collected from the central laboratory will be averaged in the case of duplicate results. Results not included for analysis will be included in listings only.

For LOCF imputation, the last evaluation on or prior to the upper bound of the specified window (ie, no lower bound) would be used for each nominal visit.

The window for the monthly phone contact in between clinic visits throughout the study is  $\pm 7$  days. The window for the end of primary analysis period phone call is  $-14$  days to end of primary analysis. Unscheduled follow-up clinic visits after the monthly phone contact have a  $+ 21$ -day window. The window for the end of study phone contact is  $-14$  days to  $+ 7$  days.

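### Month 36 BMD, a named secondary endpoint, has two conflicting analyses: an ANCOVA with LOCF (protocol, with SAP 9.2.3 keeping LOCF) and a description of observed values without LOCF (SAP 10.5.3.3)

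*SAP*

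**What the plan says.** **Endpoint.** SAP 4.2 lists "Percent change from baseline in BMD at the lumbar spine, total hip, and femoral neck at Months 24, and 36" among the secondary endpoints for the primary analysis period. Protocol 10.1.2 has the same item.

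**Protocol.** Section 10.5.2.1 (Bone Mineral Density by DXA) says: "Percent changes of BMD from baseline to Month 24 and 36 during the primary analysis period will be analyzed using the same ANCOVA approach". A missing value at either visit is "imputed by the last post-Month 12 value that is prior to the time point of interest".

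**SAP, missing data.** Section 9.2.3 says "The LOCF imputation will be done up to Month 36". It limits the source of the carried value: "the values in the double-blind period will not be carried forward into open-label period". It also says that nothing is imputed when the repeated-measures model is used. Section 13.1.1 defines the LOCF window as "the last evaluation on or prior to the upper bound of the specified window (ie, no lower bound) would be used for each nominal visit".

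**SAP, analysis.** Section 10.5.3.3 opens by naming Months 12, 24 and 36. The treatment comparisons "at months 12 and 24 will be analyzed using the ANCOVA model described in" Section 10.5.1.5, with LOCF, and Month 36 is not among them. For Month 36, a descriptive summary of "observed DXA values at Month 36 will be provided without LOCF". The repeated-measures model of 10.5.1.6 is added as a sensitivity analysis, with no list of visits.

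**Declared changes.** SAP Section 11 lists one change from the protocol, a fracture covariate in the pain analysis. The Month 36 change is not there.

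**The concern.** There are two positions on one endpoint. The protocol and SAP 9.2.3 carry values forward to Month 36, and the protocol compares the arms there. SAP 10.5.3.3 does neither. Nothing in the SAP says that the change is deliberate, so the choice could be made after the data are seen.

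Neither position is a good analysis of Month 36.

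- **LOCF.** DXA stops at the end of the primary analysis period (Protocol 7.3.18), and minimum follow-up is 24 months. Many women will have no Month 36 scan because the visit was never due. The rule fills the gap with an earlier scan and labels it Month 36.
- **Description only.** The main analysis then yields no between-arm difference and no interval for a named secondary endpoint.

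**Working it through.** **Inputs**

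- Enrolment 34 months; dropout 10% in year 1 and 8% per year thereafter (Protocol 10.2).
- Primary analysis at the last woman's Month 24, calendar month 34 + 24 = 58. Section 10.2 puts the median time after that visit, and the Amendment 5 rationale says that 330 fractures will have occurred before it.
- Accrual shape: not stated. I assume that the share enrolled by month t is (t/34)^g, where g = 1 is even, g < 1 front-loaded and g > 1 back-loaded.

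**The plan's own figure.** Protocol 3.4.1 gives 25 to 59 months per woman at primary analysis, including screening. With one month of screening, 1 + 24 = 25 and 1 + 34 + 24 = 59. It reproduces, so month 58 is the right cut-off.

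**Who can reach Month 36.** A woman must be enrolled by month 58 − 36 = 22. Under even accrual that is 22/34 = 64.7%, and 12/34 = 35.3% cannot reach it.

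**Retention**

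- To Month 24: 0.90 × 0.92 = 0.828
- To Month 36: 0.90 × 0.92² = 0.762
- Ratio: 0.92

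**Carried-forward share.** Take women with a Month 24 value as the LOCF set, and let s = (22/34)^g be the share enrolled early enough. The observed share is 0.92s, so the carried-forward share is 1 − 0.92s. The number with an observed Month 36 value is 4,000 × 0.762 × s.

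| g | s | observed at Month 36 | carried forward |
|---|---|---|---|
| 0.5 | 0.804 | about 2,450 | 26.0% |
| 1 (even) | 0.647 | about 1,970 | 40.5% |
| 1.5 | 0.520 | about 1,590 | 52.1% |
| 2 | 0.419 | about 1,280 | 61.5% |

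Under even accrual the 40.5% is 35.3% not yet due plus 0.647 × 0.08 = 5.2% lost between Months 24 and 36.

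**Sensitivity to definition.** Under even accrual the share is about 35% if early-termination scans after Month 24 count as Month 36. It is about 45% if the set is everyone with any open-label value (up to 0.90 of those randomised: 1 − 0.493/0.90).

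**Can the stated event count fix the accrual shape?** Protocol 10.2 reports a median of 396 women with clinical fracture at the primary analysis. I simulated the stated model with a control nonvertebral rate of 4% a year, and again with 4.125% (5.5% × 0.75).

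| g | median events, 4% | median events, 4.125% |
|---|---|---|
| 1 | 433 to 437 | about 444 |
| 1.5 | 402 | about 414 |
| 2 | 384 | 399 |

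Back-loaded shapes of about 1.5 to 2 fit 396 best. Other unstated choices also move the count, such as whether a rate is a hazard or an annual probability. The shape is therefore not identified.

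**Effect on the estimate.** Suppose a fraction f is carried forward from Month 24, equally in both arms and unrelated to response. The LOCF difference is then (1 − f)Δ36 + fΔ24, and its bias is f(Δ24 − Δ36). It vanishes if the arms stay equally far apart. For each percentage point by which the difference narrows from Month 24 to Month 36, LOCF overstates it by about 0.26 to 0.62 points. The documents give no Month 36 assumption, so the actual bias cannot be computed.

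**The case against.** The strongest reply is that the SAP has already settled the matter sensibly. The endpoint-specific Section 10.5.3.3 should outrank the general rule in 9.2.3. It drops LOCF at Month 36, and Section 10.7.2 likewise summarises observed Month 36 values in the sub-study. The repeated-measures model, which imputes nothing and reports differences with 95% CIs, is not restricted by visit, so a Month 36 contrast may already be planned. The code that would show this is redacted, which is no fault of the plan.

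Much of this stands, and it rules out several stronger readings.

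- **Three rival analyses.** Three sections speak to the point, but the protocol and SAP 9.2.3 agree on carry-forward. There are two positions.
- **No treatment comparison at all.** This is true of the main analysis only; the sensitivity model is silent on visits.
- **An unanswered objective.** The BMD objective covers the primary analysis period and does not name Month 36. The Month 24 comparison addresses it, inside the testing sequence.
- **Mostly Month 24 values.** The share passes half only if accrual is back-loaded. Some carried values would be early-termination or sub-study Month 18 scans.

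A further reply is that SAP 9.2 describes missing data as arising from withdrawal, missed visits or unevaluable measurements, not from visits not yet due. Filling such visits is indeed an inference. But the window has no lower bound, and SAP 7.6 admits anyone with a baseline and one later evaluation at or before the time point. As written, the rule does not exclude these women.

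What the reply does not remove is the conflict between SAP 9.2.3 and 10.5.3.3, the undeclared departure from the protocol, and the unstated visits of the sensitivity model.

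**Conclusion.** The concern holds as an inconsistency on a named secondary endpoint, and it is minor. If the protocol and SAP 9.2.3 rule is followed, roughly 26% to 62% of a Month 36 LOCF analysis would be carried forward, mostly from Month 24; even accrual gives about 40%. If SAP 10.5.3.3 is followed, the main analysis provides no treatment difference or interval.

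The range rests on the stated dropout, a primary analysis at month 58, complete scanning of women who remain, and an assumed accrual shape. No single figure within it should be presented as what the plan implies.

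A reader might infer a threat to error control or to the primary results. The documents do not support that: SAP 10.1 and 13.5 place only Month 12 and Month 24 BMD in the testing sequence.

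**What to change.** Three edits to the SAP:

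1. **Section 9.2.3.** Change the LOCF limit for DXA from Month 36 to Month 24. Do not simply delete the limit: DXA windows run to Month 60 (Section 13.1.1.2), so carry-forward would then have no upper bound.
2. **Section 10.5.3.3.** Name Month 36 as a visit in the repeated-measures model of 10.5.1.6. Report the treatment difference with its 95% CI from observed data, outside the testing sequence. Label it as resting on a missing-at-random assumption. That is plausible for women whose visit was not yet due, since their absence depends on entry date; it is a real assumption for women who withdrew.
3. **Section 11.** Record the departure from the protocol ANCOVA and the reason.

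If the sponsor prefers description only, edits 1 and 3 are still needed, and 10.5.3.3 should say that the repeated-measures model stops at Month 24.

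The cost is SAP wording and a small amount of added output. No new data, visits or alpha are required.

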#### **10.5.3.4 Change from Baseline in Height**

The subset as described in [Section 7.6](#) will be used for the analyses of change from baseline in height at months 12 and 24. A nonparametric method, Van Elteren rank test, as described in [Section 10.5.1.8](#), will be used for treatment comparisons for change from baseline in height. ANCOVA models as described in [Section 10.5.1.5](#) will also be used for treatment comparisons.

#### **10.5.4 PRO/ClinRO Exploratory Endpoints**

The subset described in [Section 7.6](#) will be used for the analysis of PRO/ClinRO endpoints and the subset described in [Section 7.7](#) will be used for the analysis of post fracture PRO endpoints.

Descriptive summary statistics will be provided for actual values and changes from study baseline by visit as described in [Section 10.5.1.4](#). Descriptive summary statistics will also be provided for the changes from the pre-fracture baseline by visit since fracture. The comparison of treatments on the post-fracture PRO data includes subjects who have a clinical fracture on study, however, the fracture type, fracture location and patient characteristics might be different in these fractured subjects between two treatment arms. Although various factors will be adjusted in the analysis, due to the lack of randomization, the comparability is not ensured and therefore the analysis is more susceptible to bias.

#### **OPAQ-SV**

The analyses of changes from study baseline at months 6, 12, 18, 24, 30, and 36 in OPAQ-SV dimension scores of physical function, emotional status, and back pain will be performed using the repeated measures model separately as described in

[Section 10.5.1.6](#). The analyses of changes from pre-fracture baseline at month 1, 2 and 3 after reporting a clinical fracture in OPAQ-SV dimension scores will be performed using the repeated measures model adjusting for age strata, presence or absence of severe vertebral fracture at baseline, treatment, visit, fracture type, pre-fracture baseline score, change from pre-fracture baseline at report of fracture and treatment by visit interaction. The missing OPAQ SV dimension scores at reporting of the fracture will be handled by multiple imputation.

#### **EQ-5D-5L**

The analyses of changes from study baseline at months 6, 12, 18, 24, 30, and 36 in EQ-5D-5L VAS score will be performed using the repeated measures model as described in [Section 10.5.1.6](#).

Each of the 5 EQ-5D-5L dimension scores (mobility, self-care, usual activities, pain/discomfort, anxiety/depression) at month 6, 12, 18, 24, 30, and 36 will be analyzed using repeated measure proportional odds model adjusting for age strata, presence or absence of severe vertebral fracture at baseline, treatment, visit, baseline score and treatment-by-visit interaction as described in [Section 10.5.1.2](#).

The change from study baseline at month 6, 12, 18, 24, 30, 36 and the change from pre-fracture baseline at month 1, 2 and 3 after fracture in 5 EQ-5D-5L dimension scores will be summarized by shift tables.

The analyses of changes from pre-fracture baseline at month 1, 2 and 3 after reporting a clinical fracture in EQ-5D-5L VAS score will be performed using the repeated measures model adjusting for age strata, presence or absence of severe vertebral fracture at baseline, treatment, visit, fracture type, pre-fracture baseline score, change from pre-fracture baseline at report of fracture and treatment by visit interaction. The missing EQ-5D-5L VAS score at reporting of the fracture will be handled by multiple imputation.

#### **BPI Worst Pain Score**

The analyses of changes from study baseline at months 6, 12, 18, 24, 30, and 36 in BPI worst pain score will be performed using the repeated measures model as described in [Section 10.5.1.6](#). The analyses of changes from pre-fracture baseline at month 1, 2 and 3 after reporting a clinical fracture in BPI worst pain score will be performed using the repeated measures model adjusting for age strata, presence or absence of severe

vertebral fracture at baseline, treatment, visit, fracture type, pre-fracture baseline score, change from pre-fracture baseline at report of fracture and treatment by visit interaction. The missing BPI worst pain score at reporting of the fracture will be handled by multiple imputation.

The proportion of subjects with a clinically meaningful improvement in worst pain in 3 months after experiencing a nonvertebral or clinical vertebral fracture (defined as a 2-point improvement in the BPI worst pain scale compared with the fracture reporting visit) will be analyzed using a logistic regression model adjusting for age strata, presence or absence of severe vertebral fracture at baseline, treatment, fracture type, worst pain score at report of fracture and change from pre-fracture baseline at report of fracture. The proportion of subjects with a clinically meaningful improvement in worst pain at each post fracture reporting visit and within 3 months from pre-fracture baseline will be analyzed using same approach.

### **LAD Questionnaire**

The number and percent of subjects reporting in the past month cutting down on things due to health reasons (Question 1), in hospital overnight due to health reasons (Question 3), and stay in bed due to health reasons (Question 4) at months 6, 12, 18, 24, 30, and 36, and at month 1, 2 and 3 after fracture will be summarized descriptively. Subjects reporting cutting down things but with missing value for number of days will not be included in the respective analysis of number of days.

Number of days in the past month of cutting down things due to health reasons (Question 2a), in hospital overnight due to health reasons (Question 3a), and stay in bed due to health reasons (Question 4a) at months 6, 12, 18, 24, 30, and 36 will be summarized descriptively. The treatment comparison at months 6, 12, 18, and 24, will be done using the repeated measures model adjusted for age strata, presence or absence of severe vertebral fracture at baseline, treatment, visit, treatment by visit interaction, and baseline.

Number of days in the past month of cutting down on things due to a fracture (Question 2b), in hospital overnight due to a fracture (Question 3b), and stay in bed due to a fracture (Question 4b) at month 1, month 2 and month 3 after fracture will be summarized descriptively in subjects who have a fracture during the 12-month double-blind period. The treatment comparison will be done using the repeated

measures model adjusted for age strata, presence or absence of severe vertebral fracture at baseline, treatment, visit, treatment by visit interaction, fracture type, pre-fracture baseline and change from pre-fracture baseline at report of fracture.

Change from pre-fracture baseline in number of days in the past month of cutting down things due to health reasons, in hospital overnight due to health reasons, and stay in bed due to health reasons at month 1, month 2 and month 3 after fracture and each first post fracture visit will be summarized descriptively in subjects who have a fracture during the 12-month double-blind period. The treatment comparison will be done using the repeated measures model adjusted for age strata, presence or absence of severe vertebral fracture at baseline, treatment, visit, fracture type, pre-fracture baseline, change from pre-fracture baseline at report of fracture and treatment by visit interaction.

Change from pre-fracture baseline in number of days in the past month of cutting down things due to a fracture, in hospital overnight due to a fracture, and stay in bed due to a fracture at fracture reporting visit and each first post fracture visit will be summarized descriptively in subjects who have a fracture during the 12-month double-blind period. The treatment comparison will be done using the repeated measures model adjusted for age strata, presence or absence of severe vertebral fracture at baseline, treatment, visit, fracture type, pre-fracture baseline, change from pre-fracture baseline at report of fracture and treatment by visit interaction.

